4.4.1.4 Vital signs

All vital sign data collected will be listed.

Mean absolute values and mean change from baseline for BP will be summarised by treatment, and time point; graphical presentation of mean change from baseline and SE will be provided also.

High and low PCS vital signs values will be identified. Vital sign values will be PCS if they meet both the PCS criteria for the observed value and the PCS criteria for the change from baseline value for criterion 1, or if they meet the PCS criteria for the observed value for criterion 2; the 2 criteria should not be combined. The criteria for PCS vital signs values are displayed in Table 6.

Table 6 PCS vital sign criteria

		Criterion 1		Criterion 2
Vital sign		Observed value	Change from baseline	Observed value
Systolic BP (mmHg)	High	≥ 180	Increase of ≥ 20	≥ 200 , if baseline < 160
	Low	≤ 90	Decrease of ≥ 20	≤ 75 , if baseline > 75
Diastolic BP (mmHg)	High	≥ 105	Increase of ≥ 15	≥ 115 , if baseline < 115
	Low	≤ 50	Decrease of ≥ 15	≤ 40 , if baseline > 40

BP = Blood pressure.

The number and percentage of patients with post-baseline PCS vital sign values will be summarised for each criteria by treatment, day and timepoint within day. Percentages will be based on the number of patients with baseline vital sign values and at least one post-baseline vital sign assessment.

A listing of individual data for all patients with PCS vital sign values will be provided, and will include treatment sequence, patient number, and all vital sign values (baseline and post-baseline values).

A listing of all treatment-emergent AEs recorded for patients with PCS vital sign values (at baseline or post-baseline) will also be provided.

CCI

[REDACTED]

[REDACTED]

CCI

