3. PRIMARY AND SECONDARY VARIABLES

3.1 General definitions

Baseline for FEV₁ will be defined as the mean of the 2 measured values for the corresponding variable (2 measurements 45 min apart, at -1 hour and -15 min), prior to the morning IP administration on Day 1 of each treatment period. If both are missing, the Visit 2 pre-bronchodilator value will be used instead. If one of the values is missing, the available value will be used as baseline.

All baseline values for efficacy analysis will be the pre-dose values of each treatment period except for the Total BCSS questionnaire score, where the last 14 days of the run-in period baseline will be used for all treatments in each sequence.

The baseline for daily rescue medication use will be the daily average of puffs recorded in the e-Diary during the last 14 days of the run-in period; this baseline will be used as baseline for all treatment periods.

For vital signs, laboratory variables (including i-STAT) and 12-lead ECG variables, baseline is defined as the values obtained prior to the morning IP administration on Day 1 of Visit 3.

The cough VAS measurement done at pre-dose on Day 1 of each treatment period will be used as a baseline. For cough monitoring, the assessment done starting 24 hours prior to dosing on Day 1 will be regarded as a baseline of each treatment period.

For COPD assessments (CAT), baseline is defined as the value obtained at Screening (Visit 1 or Visit 2).

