4.4.1.3 ECG

All ECG data collected will be listed.

Mean absolute values and mean change from baseline for continuous ECG parameters will be summarised by treatment, day (Day 1, 8, and 14) and timepoint within day, 95% CIs for the change from baseline will be provided in addition to the usual descriptive statistics parameters.

Graphical presentation of mean change from baseline (and SE) for ECG parameters by treatment and timepoint will also be provided.

For HR, and QTcF parameters, change from baseline at each timepoint within Day 1, Day 8, and Day 14 will be analysed by means of a mixed model; a random effect model with fixed effects for treatment, sequence, and period. The patient will be fitted as a random effect and the pre-dose value of the parameter obtained at visit 3 will be included as a covariate. Between-groups difference in LSM means will be provided with their 90% CI. A Figure presenting the LSM means and 90% CI across time will be presented as well.

QTcF exceeding ICH boundaries are defined in Table 4. Other ECG values (HR, QRS interval, and PR interval) are defined to be PCS if they meet criterion 1 or criterion 2 displayed in Table 5. Number and percentages of patients with post-baseline QTcF exceeding ICH boundaries and PCS ECG values will be presented for each category, each criterion defined in Table 4 and Table 5.

These numbers and percentages of patients with post-baseline QTcF exceeding ICH boundaries and PCS ECG values will be summarised by treatment overall and by timepoint within each day (Day 1, 8, and 14).

A listing of individual data for all patients with PCS ECG values will be provided, and will include treatment sequence, patient number, and all ECG values (baseline and post-baseline values), clinical relevance of PCS assessed by the PI will also be in the listing.

A listing of all treatment-emergent AEs recorded for patients with PCS ECG values (at baseline or post-baseline) will also be provided.

The number and percentage of patients with post-baseline abnormal ECG findings (Rhythm, Extra Systoles, Conduction, ST-Changes, ST Segment, T Wave Observations, and U Wave Observations) will be summarised by treatment, overall and by timepoint within each day (Day 1, 8, and 14).

Percentages will be based on the number of patients with at least one post-baseline ECG assessment.

A listing of all ECG abnormal findings will be provided.

Table 4 PCS ECG criteria: QTcF exceeding ICH boundaries

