
Category 1: QTcF value above the following cut-off at any time during treatment
 
Criteria:
 
 >450 (ms) >480 (ms) >500 (ms) 
Category 2: QTcF increase by more than following cut-off at any time during treatment
 
Criteria:
 
 >30 (ms) >60 (ms) >90 (ms) 
Category 3: QTcF value above cut-off and QTcF increase by more than cut-off at any time during treatment
 
Criteria:
 
 Value >450(ms) and Increase >30(ms) Value >500(ms) and Increase >60(ms)
--

Table 5 PCS ECG criteria: Heart Rate and QRS interval

ECG parameter	Category	Criterion 1	Criterion 2
Heart rate	Tachycardia event	≥ 110 bpm and an increase of $\geq 15\%$ over baseline value	≥ 120 bpm if baseline is < 100 bpm
	Bradycardia event	≤ 50 bpm and a decrease of $\geq 15\%$ over baseline value	≤ 40 bpm if baseline is > 40 bpm
QRS interval		≥ 100 msec and an increase of $\geq 25\%$ over baseline value	≥ 150 msec if baseline is < 150 msec
PR interval		≥ 200 msec and an increase of $\geq 25\%$ over baseline value	≥ 250 msec if baseline is < 250 msec

bpm = beats per minute.

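### In SAP Tables 5 and 6, criterion 2 for tachycardia and for high systolic pressure uses a lower baseline limit than the other six rows, so it flags no additional patient and misses some extreme values

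*SAP*

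**What the plan says.** SAP 4.4.1.3 states that heart rate, QRS and PR values "are defined to be PCS if they meet criterion 1 or criterion 2 displayed in Table 5". SAP 4.4.1.4 applies the same either/or rule to blood pressure. Values qualify "if they meet both the PCS criteria for the observed value and the PCS criteria for the change from baseline value for criterion 1", or alternatively "if they meet the PCS criteria for the observed value for criterion 2; the 2 criteria should not be combined". Both sections report patient counts separately for each criterion.

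Criterion 1 needs an absolute level and a change from baseline. Criterion 2 needs a more extreme level and sets a limit on the baseline. For tachycardia the criterion 2 cell is 120 "bpm if baseline is < 100 bpm" or above; for high systolic pressure it is 200 mmHg or above "if baseline < 160".

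Baseline is defined in two ways. SAP 3.1 says that for vital signs, laboratory and ECG variables "baseline is defined as the values obtained prior to the morning IP administration on Day 1 of Visit 3". SAP section 6 instead takes the last assessment before the first dose of each period.

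**The concern.** In the other six rows the criterion 2 baseline limit equals the cut-off, so any crossing of the extreme threshold is counted. The two exceptions are tachycardia, which protocol 2.3 names as a potential risk, and high systolic pressure. Protocol 2.3 also reports heart rate as the only safety outcome with a dose response in the earlier multiple-dose study in healthy subjects, and asks for it to be explored further.

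With the lower limits, criterion 2 in these two rows cannot add a patient to those already PCS under criterion 1, and its own count leaves out some values at or above its cut-off. A smaller set of such values meets neither criterion. A patient whose only notable value lies in that set would be absent from the PCS tables, the PCS listing, and the listing of adverse events for patients with PCS values.

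**Working it through.** The plan states no figure to reproduce; this is a check of which values satisfy which rule.

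**Inputs (SAP Tables 5 and 6).**

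| Row | Criterion 1 | Criterion 2 cut-off | Baseline limit |
|---|---|---|---|
| Tachycardia | ≥110 bpm and rise ≥15% | ≥120 | <100 |
| Bradycardia | ≤50 bpm and fall ≥15% | ≤40 | >40 |
| QRS | ≥100 ms and rise ≥25% | ≥150 | <150 |
| PR | ≥200 ms and rise ≥25% | ≥250 | <250 |
| Systolic, high | ≥180 mmHg and rise ≥20 | ≥200 | <160 |
| Systolic, low | ≤90 mmHg and fall ≥20 | ≤75 | >75 |
| Diastolic, high | ≥105 mmHg and rise ≥15 | ≥115 | <115 |
| Diastolic, low | ≤50 mmHg and fall ≥15 | ≤40 | >40 |

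Write b for baseline and v for the post-baseline value.

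**Step 1: does criterion 2 add anyone?**
- Tachycardia: b < 100 and v ≥ 120 give v/b > 120/100 = 1.20. The rise exceeds 20% and v exceeds 110, so criterion 1 is always met.
- High systolic: b < 160 and v ≥ 200 give v − b > 200 − 160 = 40. The rise exceeds 20 mmHg and v exceeds 180, so criterion 1 is always met.

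Enumerating integer pairs (heart rate 30–220 bpm, systolic 60–260 mmHg) agrees: 7,070 heart-rate pairs and 6,100 systolic pairs meet criterion 2, and none of either fails criterion 1. In each of the other six rows some pairs meet criterion 2 only, for example PR 201 to 250 ms (49/201 = 24.4%, below 25%) and diastolic 101 to 115 mmHg (+14, below 15).

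**Step 2: what does the criterion 2 count omit?** By its limits, every value ≥120 bpm from a baseline of 100–119, and every value ≥200 mmHg from a baseline of 160–199, whether or not criterion 1 catches it.

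**Step 3: what meets neither criterion?**
- Heart rate: b ≥ 100, v ≥ 120 and v < 1.15b. At v = 120 this needs b > 120/1.15 = 104.3. Threshold crossings are therefore missed from integer baselines 105–119. Examples: 105 to 120 (15/105 = 14.3%) and 119 to 136 (17/119 = 14.3%). A baseline of 104 is caught: 16/104 = 15.4%.
- Systolic: b ≥ 160, v ≥ 200 and v − b < 20. At v = 200 this needs b > 180, so crossings are missed from 181–199. Examples: 181 to 200 (+19) and 185 to 204 (+19). A baseline of 180 is caught: 200 − 180 = 20.

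The neither-criterion gap therefore starts at 105 bpm and 181 mmHg, not at the limits of 100 and 160.

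**Step 4: can such baselines occur?** Protocol 5.2 excludes a heart rate above 100 bpm and hypertension above 160 mmHg that the investigator judges uncontrolled and clinically significant. Baselines of 105 or 181 should therefore be rare at Visit 3. The stability checks before periods 2 and 3 (protocol 8.1.2) set no heart-rate or blood-pressure limit, so the gap arises mainly there, and only if the per-period baseline of SAP section 6 applies.

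**Step 5: effect of aligned limits.** With <120 bpm and <200 mmHg, criterion 2 adds 139 heart-rate pairs (from 105 to 120 upward) and 190 systolic pairs (from 181 to 200 upward) on the same grids, and no upward crossing of either cut-off escapes. Further rises from baselines already at or above the cut-off stay unflagged unless criterion 1 is met, as in the upward sibling rows. Pair counts depend on the grid and say nothing about how many patients are involved; the zeros in step 1 do not depend on the grid.

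**The case against.** The strongest reply is that criterion 2 is a severity tier. Protocol 9.4.2 leaves severity-based ECG criteria to the SAP, counts are shown per criterion, and the QTcF cut-offs in Table 4 are nested too (>450, >480, >500 ms). On that view a criterion 2 lying wholly inside criterion 1 is no fault. This stands as far as it goes. A reader might infer that criterion 2 was designed to rescue extreme values that fail the change requirement, so that nesting alone proves an error; neither document states that purpose. But the tier reading does not explain these two rows, because the tier leaves out part of its own extreme range (step 2), and the SAP gives no reason for treating them differently.

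Second, every value meeting neither criterion is a rise below 15% or below 20 mmHg, which is small by the SAP's own standard, and aligned limits would flag 119 to 120 bpm. That is a fair cost, but the other six rows already accept one-unit crossings.

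Third, the safety assessment does not hang on these flags. All ECG and vital-sign data are listed, heart-rate change is modelled at each time point with 90% intervals, and blood-pressure means and changes are summarised and plotted. This stands, and it limits the importance of the point.

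**Conclusion.** The point holds as a minor inconsistency in two reporting rows. Criterion 2 for tachycardia and for high systolic pressure adds no PCS patient, its separate count omits part of the range above its cut-off, and crossings from 105–119 bpm with a rise below 15%, or from 181–199 mmHg with a rise below 20 mmHg, are not flagged.

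The number of patients cannot be calculated, because the documents give no distribution of pre-dose heart rate or systolic pressure. That few are affected is an inference: it assumes that the entry limits largely hold at Visit 3 and that pre-dose values of 105 bpm or 181 mmHg are uncommon later. Whether the gap can open in periods 2 and 3 depends on which SAP baseline definition governs.

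A reader might go further and conclude that extreme values vanish from the report or that a tachycardia signal would be concealed. The documents do not support that, given the full listings and the separate heart-rate model. No efficacy result is touched.

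**What to change.** Before unblinding, align the criterion 2 baseline limits with the other six rows: <120 bpm for tachycardia in Table 5 and <200 mmHg for high systolic pressure in Table 6. If the lower limits are deliberate, state the reason in the SAP. Separately, reconcile SAP 3.1 with SAP section 6 so that one baseline definition governs these tables.

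The first change costs two table cells and the matching program conditions, with no new data. Its downside is that small crossings at the threshold would be flagged. It concerns reporting flags only and leaves the protocol's withdrawal criteria and patient management as they are.

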5. INTERIM ANALYSES (NOT APPLICABLE)

6. CHANGES OF ANALYSIS FROM PROTOCOL

Change in the analysis set used:

All demographic and baseline characteristics will be analysed using the full analysis set instead of the safety population.

Change in definition of baseline for vital signs, laboratory variables including i-STAT glucose and potassium and ECG variables:

Baseline is defined as the last assessment made before the first dose of IP in each period instead of the value obtained prior to the morning IP administration on day 1 of Visit 3

For HR, and QTcF parameters:

Analyses of change from baseline at each day and timepoint within day will be performed instead of the analysis of AUC₀₋₄ at Day 1, Day 8, and Day 14 and AUC₀₋₂₄ at Day 1 and Day 14. No formal analysis of other ECG parameters will be performed.

Dropouts due to lack-of-efficacy during treatment periods added as a COPDCompEx event.

Additional analysis on FEV1:

Statistical analyses on the change from baseline in FEV1 15 min, 30 min, 1, 2, 4, 8, 23, and 23:45 hours post-dose will be presented by treatment group at Day 1 and Day 15.

Also, analyses on the change from baseline in FEV1 15 min, 30 min, 1, 2, and 4 hours post-dose will be presented by treatment group at Day 8.

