Study D6640C00005 was a Phase I, randomised, multiple ascending dose (MAD) study to investigate safety, tolerability and PK of AZD8871 in healthy male Japanese subjects. This study entailed 3 dose levels: 300 µg (cohort 1), 600 µg (cohort 2) and 900 µg (cohort 3). In this study, the administration schedule for AZD8871 or placebo was a single dose on Day 1, followed by once daily dosing from Day 5 to Day 16 (12 consecutive daily doses). Safety stopping criteria or pre-set exposure limits were not reached. Overall, single and multiple doses of AZD8871 administered to healthy male subjects in this study were well tolerated and no safety concerns were noted for any of the dosages investigated.

To limit the risks for the patients enrolled in this study D6640C00006 and who will be required to stop their usual COPD therapy and to assess IP efficacy, patients will be maintained on a mono-component ICS, if required. They will also be provided with salbutamol 100 µg to be used as rescue medication. In addition, patients that were taking any LAMA and/or LABA will be maintained with ipratropium between Visit 1 and Visit 2. All patients will receive ipratropium (20 µg × 2 puffs 4 times per day) during run-in and wash-out period to ensure stability of the patient.

Potential risks have been evaluated through review of the literature regarding β₂-agonists and muscarinic antagonists, AZD8871 non-clinical studies, and data from completed or ongoing

AZD8871 clinical studies. Relevant potential risks include cardiac effects (such as tachycardia, PR interval prolongation and 1st and 2nd degree atrio-ventricular blocks); other potential risks are metabolic effects (such as hyperglycemia and hypokalaemia) and hypersensitivity. No treatment-related serious or severe AEs have been reported in the completed or ongoing clinical studies. No clinically significant ECG abnormalities or laboratory abnormalities were observed to date in human trials. Thus, AZD8871 was well tolerated in firsts in human trials and its safety profile is acceptable for continuing further investigations.

More detailed information about the known and expected benefits and risks and reasonably expected AEs of AZD8871 may be found in the IB.

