4.4.1.2 Laboratory data

All laboratory data recorded in the eCRF will be listed. Flags will be applied to values falling outside the expanded normal ranges (which will be explicitly noted on these listings where applicable). Individual patient data where ALT and/or AST and total bilirubin are elevated at any time will be listed (ie, ALT and/or AST $\geq 3 \times$ the upper limit of normal [ULN] and total bilirubin $\geq 2 \times$ ULN, at any time) to evaluate potential Hy's Law cases.

Change from baseline to 24h post-dose assessment will be calculated.

For i-STAT glucose and potassium at Day 1 and 14, mean absolute values at baseline, 1, 2, 4, and 24 hours postdose as well as mean changes from baseline at 1, 2, 4, and 24 hours post-dose will be presented by treatment.

Mean absolute values and mean change from baseline for all clinical chemistry and haematology laboratory parameters (in international system of units [SI]) will be presented by treatment and timepoint.

A figure summarizing the mean change from baseline (and SE) in i-STAT glucose and potassium by treatment and timepoint will also be provided.

Shift from baseline tables will be presented by treatment overall and by timepoint, separately for haematology, clinical chemistry and iSTAT measurements, showing the number and percentage of subjects with shifts from baseline for each laboratory variable.

Shift is defined as the change in category based on the expanded normal ranges (low, normal or high as above) at baseline to a post-baseline timepoint. The number and percentage of patients with laboratory test values:

- lower than the lower limit of the expanded normal range (ENR),
- within the ENR limits, and
- larger than the upper limit of the ENR

will be provided for post baseline timepoints, the ENR being calculated by multiplying the LLN and ULN of the laboratory by the factor shown in Table 3.

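### PR interval, potassium and glucose, which the protocol names as risks, are summarised by treatment only; among safety variables the crossover treatment difference with a CI is kept for heart rate and QTcF

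*SAP*

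**What the plan says.** Protocol 2.3 (Benefit/risk assessment) sets out the risks: "Relevant potential risks include cardiac effects (such as tachycardia, PR interval prolongation and 1st and 2nd degree atrio-ventricular blocks"; and "other potential risks are metabolic effects (such as hyperglycemia and hypokalaemia) and hypersensitivity".

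For safety data, the SAP plans a between-treatment comparison for two variables. Section 4.4.1.3 states: "For HR, and QTcF parameters, change from baseline at each timepoint within Day 1, Day 8, and Day 14 will be analysed", by a mixed model with treatment, sequence and period as fixed effects and patient as random effect, giving LS mean differences with 90% CIs. SAP 3.5.5 likewise limits between-group differences to heart rate and QTcF. SAP 6 closes the matter for the rest of the ECG: "No formal analysis of other ECG parameters will be performed".

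PR is covered in SAP 4.4.1.3 by means and mean changes by treatment, 95% CIs for the change, counts of potentially clinically significant (PCS) values under Table 5, counts of abnormal conduction findings, and listings.

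For i-STAT potassium and glucose, SAP 4.4.1.2 says that "mean changes from baseline at 1, 2, 4, and 24 hours post-dose will be presented by treatment". It adds a figure of mean change with SE, shift tables, and tables of new, worsened and notable abnormalities using the Table 3 limits.

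**The concern.** In a crossover each patient is their own control, and the useful safety quantity is the within-patient difference between treatments. Protocol 4.2 says the placebo arm was added partly to describe the product's safety better and to help interpret differences in safety outcomes. SAP 4.1.1 says the purpose is to estimate rather than to test. For three risks that the protocol names, the planned tables stop short of that estimate.

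A reader who wants AZD8871 minus placebo for PR would have to subtract two columns. The SE of that subtraction cannot be recovered correctly from the columns, because the within-patient correlation is not shown. The columns may also describe somewhat different patients: SAP 2.1.2 counts a patient under a treatment only if they took it, Protocol 9.2 allows for about 25% dropout, and Protocol 2.3 reports that 31 of 42 patients completed the earlier three-way crossover.

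**Working it through.** **1. What each variable gets**

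| Variable | Named in the Protocol 2.3 risk list | Output by treatment | Treatment difference with CI |
|---|---|---|---|
| Heart rate | Yes (tachycardia) | Yes | Yes, 90% |
| QTcF | No (QTc appears earlier in 2.3 as a class effect of β2-agonists) | Yes | Yes, 90% |
| PR | Yes | Means, changes, PCS and conduction counts | None |
| i-STAT potassium | Yes | Means, changes, shift and abnormality tables | None |
| i-STAT glucose | Yes | Means, changes, shift and abnormality tables | None |

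SAP 4.1.2 says an unadjusted CI is used where no model is fitted. That is a presentation rule; it does not plan a treatment difference for the last three rows.

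**2. The plan's own figure**

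Protocol 9.2: difference 100 mL, SD of differences 220 mL, n = 54, two-sided 5%.
- Normal approximation: (100/220) × √54 = 3.340; 3.340 − 1.960 = 1.380; power 91.6%.
- Paired t with 53 df: 90.6%.
- 54/(1 − 0.25) = 72.

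The stated 90% and 72 reproduce, and they rest on a within-patient comparison. No such figure is given for PR, potassium or glucose.

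**3. Precision available for PR**

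The documents give no SD for PR. Assume a within-patient SD s of 8 to 12 ms and use the paired formula for 54 completers:

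half-width = t(0.95; 53) × s × √(2/54) = 1.674 × 0.1925 × s = 0.322 s

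- s = 8: 2.6 ms
- s = 10: 3.2 ms
- s = 12: 3.9 ms

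**4. Gain over subtracting two columns**

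With σ the per-treatment SD of the change and ρ the within-patient correlation (both unknown here), the SE of the difference is σ√(2(1 − ρ)/n) within patient, against σ√(2/n) if the pairing is ignored. The ratio is √(1 − ρ). The 90% half-width from two columns is 0.319 σ at n = 54.

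| Assumed ρ | Within-patient 90% half-width | SE ratio |
|---|---|---|
| 0 | 0.322 σ | 1.00 |
| 0.3 | 0.270 σ | 0.84 |
| 0.5 | 0.228 σ | 0.71 |
| 0.7 | 0.176 σ | 0.55 |
| 0.8 | 0.144 σ | 0.45 |

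The SE is 16% to 55% smaller over ρ = 0.3 to 0.8, with no gain at ρ = 0.

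**5. Where Table 5 first flags PR**

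Criterion 1 needs at least 200 ms and a rise of at least 25%. Criterion 2 needs at least 250 ms from a baseline below 250 ms. For baselines below 200 ms the first flagged value is max(200, 1.25 × baseline), since 1.25 × baseline then stays below 250.

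| Baseline (ms) | First flagged value (ms) | New values of 200 ms or more not flagged |
|---|---|---|
| 160 or less | 200 | none |
| 175 | 218.75 | 200 to below 218.75 |
| 185 | 231.25 | 200 to below 231.25 |
| 195 | 243.75 | 200 to below 243.75 |

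In whole milliseconds the gap applies to baselines of 161 to 199 ms.

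**6. Size of the extra analysis**

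Under Protocol Table 1, footnotes h and k, post-baseline PR times are 4 on Day 1, 2 on Day 8 and 5 on Day 14, which makes 11. i-STAT is not done on Day 8, so potassium and glucose have 4 + 5 = 9 times each. Modelling every time means 11 + 9 + 9 = 29 fits and, with two comparisons, 58 intervals. With no true effect, 0.10 × 58 = 5.8 would be expected to exclude zero. At one time per day on Days 1 and 14 the total is 3 variables × 2 days × 2 comparisons = 12 intervals (1.2 expected); at two times per day it is 24 (2.4 expected).

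**The case against.** The case for leaving the plan alone has substance. Protocol 2.3 gives a reason to single out heart rate: in the multiple-dose study in healthy subjects it was the only safety outcome with a dose response, and further exploration was requested. The PR and AV-block findings came from dogs, at a peak concentration four times that seen at the highest dose in Part 1 of D6640C00001, and no clinically significant ECG or laboratory abnormalities had been observed in human trials. Descriptive safety analysis is defensible in an exploratory Phase IIa study.

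Table 5 is also not the only route for PR. Under Protocol 8.2.4 the investigator documents conduction abnormalities, and SAP 4.4.1.3 counts them by treatment and time, so a new AV block can appear there whatever the PR rule does.

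Finally, modelling every scheduled time would add many unadjusted intervals, and the model cannot simply be copied. SAP 3.1 and 4.4.1.3 use the Visit 3 value as baseline, whereas SAP 6 uses the last value before the first dose of each period.

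What stands: the current choice is defensible, blanket modelling is not warranted, and the baseline must be settled first (heart rate and QTcF need that in any case). What does not stand: none of these outputs supplies a treatment difference with a CI, and a few pre-chosen times keep the number of intervals small. The risk list in Protocol 2.3 was written with the human data in view and still names all three.

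**Conclusion.** The gap is real but modest. PR, i-STAT potassium and i-STAT glucose have no planned within-patient difference between AZD8871 and either comparator, although heart rate and QTcF do.

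Three stronger readings are tempting and are not supported:
- A reader might infer from SAP 6 that a planned PR analysis was removed. Protocol 9.4.2 makes safety descriptive and reserves mixed models for heart rate and QT data; against it, the sentence drops formal analysis of QT and QTcB. It concerns the ECG only and says nothing about potassium or glucose.
- A reader might infer that these risks get nothing beyond means. They also get outlier and finding counts, shift tables and abnormality tables.
- A reader might infer that the trial could not produce the differences. The data are collected and listed, so the differences can be computed; they are simply not pre-specified.

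The sizes depend on assumptions. The PR half-width of 2.6 to 3.9 ms assumes a within-patient SD of 8 to 12 ms and uses a paired formula on 54 completers rather than the mixed model. The gain of 16% to 55% assumes ρ between 0.3 and 0.8. No SD was assumed for potassium or glucose, so no size in their own units is offered. The Table 5 gap needs no assumption beyond which baseline definition applies. This is a cheap improvement, not an error that threatens the trial's conclusions.

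**What to change.** 1. Reconcile the baseline for ECG and laboratory variables across SAP 3.1, 4.4.1.3 and 6 before anything else.
2. In SAP 4.4.1.2 and 4.4.1.3, apply the heart-rate/QTcF mixed model to change from baseline in PR, i-STAT potassium and i-STAT glucose at a few post-dose times on Day 1 and Day 14, named before unblinding. Report AZD8871 minus placebo and AZD8871 minus Anoro with 90% CIs, labelled as unadjusted estimates.
3. Amend the closing sentence on ECG analysis in SAP 6 so that PR is excepted.
4. Add to the Table 5 summaries the number and percentage of patients with PR of at least 200 ms whose baseline was below 200 ms. The 200 ms value is already in Table 5.

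No new data or visits are needed. The cost is some programming and table space, plus about 12 to 24 further unadjusted intervals at one or two times per day, of which one or two would be expected to exclude zero by chance.
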